9.3 OTHER ENDPOINTS

9.3.1 Pharmacokinetics and Immunogenicity

9.3.1.1 Sampling time

Samples for PK analysis will be collected pre dose (within 2 hours before each dose administration) during Visits 2, 4, 5, 6 and 7.

Pharmacokinetics samples during Visit 8 will be collected in the morning.

Anti-SAR156597 antibodies (ADA) samples will be collected at approximately the same times as the PK samples. An additional ADA sample will be collected at Visit 1.

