11.3.3 Anti-SAR156597 antibody (ADA) population

The anti-SAR156597 antibody analysis will be performed on all randomized and treated patients (safety population) with at least 1 post dose ADA sample with a reportable result. Patients will be analyzed according to the treatment actually received.

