11.4.4 Analysis of immunogenicity

The analysis of immunogenicity will be performed on the ADA population. It will include summaries for ADA prevalence, treatment-boosted ADA incidence, treatment-induced ADA incidence and kinetics of the immune response in patients with treatment-induced ADAs. Impact on PK, efficacy and safety will be assessed. Further details will be provided in the SAP.

Please refer to [Section 9.3](#) for the detection of ADA.

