2 STATISTICAL AND ANALYTICAL PROCEDURES

2.1 ANALYSIS ENDPOINTS

2.1.1 Demographic and baseline characteristics

The baseline value is defined as the last available value before the first administration of the Investigation Medicinal Product (IMP).

All baseline safety and efficacy parameters are presented along with the on-treatment summary statistics in the safety and efficacy sections ([Section 2.4.4](#) and [Section 2.4.5](#)).

Demographic characteristics

Demographic variables are gender (Male, Female), ethnicity (Hispanic or Latino, Not Hispanic or Latino, Not reported, Unknown), race (American Indian or Alaska Native, Asian, Black or African American, Native Hawaiian or other Pacific Islander, White, Not reported, Unknown), age in years (quantitative and qualitative variable: <45, [45-65[, [65-75[and ≥ 75 years) and Body Mass Index (BMI) in kg/m² (quantitative variable and qualitative variable: <30 and ≥ 30).

Medical or surgical history

Medical (or surgical) history includes previous relevant medical and surgery history collected at baseline.

This information will be coded using the version of Medical Dictionary for Regulatory Activities (MedDRA) currently in effect at Sanofi at the time of database lock.

Disease characteristics at baseline

Specific disease history includes disease duration from the time of first non-Raynaud's phenomenon manifestation (months), any systemic sclerosis history and mRSS at baseline. The auto-antibodies specific to systemic sclerosis (centromere antibodies, RNA polymerase III antibody, Scl-70 antibody and ANA staining pattern) and stratification factor (with/without medical history of SSc-ILD) as per IRT and as per electronic case report form (e-CRF) will be also presented.

Alcohol habits at baseline

Alcohol habits (frequency of alcoholic drinks in the last 12 months (Never/At least monthly/At least weekly/At least daily/Occasionally), number of standard drinks (1 or 2/Greater than 2 where standard drink means 1 pint/bottle of beer, 1 glass of wine, 1 shot of hard liquor...) per day when drinking alcohol.

Other baseline characteristics

Other baseline characteristics include weight in kilograms (quantitative variable and qualitative variable: <50, [50-100[, ≥100).

Any technical details related to computation, dates, and imputations for missing dates are described in [Section 2.5](#).

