2.1.7 Immunogenicity variables

All measurements (scheduled or unscheduled) will be assigned to analysis windows defined in [Section 2.5.4](#), in order to provide an assessment of the Anti-SAR156597 antibodies (ADA) parameter at each time point planned to be collected as per protocol.

ADA positive patients are patients with at least 1 treatment-induced or treatment-boosted ADA positive sample during the TEAE period, where:

- Treatment induced ADAs: ADAs developed de novo (seroconversion) following administration of the biotherapeutic (ie, formation of ADAs any time after the initial drug administration in a subject without pre-existing ADAs). If the baseline ADA sample is missing or non-reportable and at least one reportable ADA sample is available during the treatment (including follow-up period) the baseline sample will be considered as “negative” for data analysis. This is considered being a conservative approach for ADA assessment.

- Treatment boosted ADA: Pre-existing ADAs that were boosted to a higher level following administration of biotherapeutic (ie, any time after the initial drug administration) the ADA titer is significantly higher than the baseline titer. A low serial dilution schema (2-fold or 3 fold) should be applied during titration. A difference in titer values of two titer steps between an on treatment or follow-up sample and its baseline sample is considered significant. For examples, at least a 4-fold increase in titers for 2-fold serial dilution schema (or 9-fold increase in titers for 3-fold serial dilution schema). If no titer could be determined for a positive sample, the titer will be reported as the MRD of the assay.

The rest will be classified as ADA negative or inconclusive patients.

The following variables will be described:

- ADA response (Positive, Negative or inconclusive). For ADA positive:
 - Titer levels,
 - Neutralizing status (Positive or inconclusive).
- Pre-existing positive ADA defined as patients with positive ADA response at baseline with less than a specific increase (depending on titer calculation, eg, 4-fold increase in titer for 2-fold serial dilution schema, 9-fold increase in titer for 3-fold serial dilution schema) in the post-baseline period.

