2.3.3 Anti-SAR156597 antibody (ADA) population

The anti-SAR156597 antibody analysis will be performed on all randomized and treated patients (safety population) with at least one baseline and post dose ADA sample with a reportable result. Patients will be analyzed according to the treatment actually received.

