2.4.7 Analyses of immunogenicity data

The following summaries will be performed on the ADA population, taking into account all samples regardless of timing in relation to injections:

- ADA results (negative, positive or inconclusive) by time point and by treatment arm.
- Neutralizing status (inconclusive or positive) for positive ADA by time point and by treatment arm.

- ADA titers using descriptive statistics (median, Q1, Q3, minimum and maximum) for positive ADA by time point and by treatment arm.
- Number (%) of patients with pre-existing ADA and number (%) of patients with treatment-emergent ADA positive response by treatment arm.
- Number (%) of patients with persistent/transient/indeterminate treatment-emergent ADA positive response by treatment arm.
- Time to onset of treatment-emergent ADA positive response (in days) using descriptive statistics by treatment arm and also according to peak titer.
- Duration of ADA (in days, only for subjects with at least 2 positive ADA samples) using descriptive statistics by treatment arm.

Correlations between ADA parameters (eg, titers, treatment-emergent ADA positive status, neutralizing status) and PK, safety and/or main efficacy endpoint(s) will be explored (eg, scatter plot) according to the study results.

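### As naturally read, the SAP's ADA population leaves out the patients its missing-baseline rule is written for; the effect is small and the texts need reconciling

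*SAP*

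**What the plan says.** SAP 2.1.7 defines treatment-induced ADA and then provides for an absent baseline. The trigger is "If the baseline ADA sample is missing or non-reportable and at least one reportable ADA sample is available during the treatment" or follow-up; the baseline is then taken as negative. The reason given is "This is considered being a conservative approach for ADA assessment".

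SAP 2.3.3 builds the ADA population from safety-population patients "with at least one baseline and post dose ADA sample with a reportable result".

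SAP 2.4.7 states: "The following summaries will be performed on the ADA population, taking into account all samples regardless of timing in relation to injections". No other population is named for an ADA analysis.

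Protocol 11.3.3 has the wider population, safety-population patients "with at least 1 post dose ADA sample with a reportable result", and Protocol 11.4.4 says "The analysis of immunogenicity will be performed on the ADA population".

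On sampling, Protocol 9.3.1.1 schedules ADA samples alongside the PK samples from Visit 2 onward and adds: "An additional ADA sample will be collected at Visit 1". SAP 2.1.1 gives the general baseline definition, the last value available before first dosing.

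**The concern.** A rule for patients without a usable baseline has a purpose only if those patients are in the analysis set. SAP 2.3.3 appears to remove them. A treated patient with no reportable pre-dose sample who tests positive on treatment would then leave both the numerator and the denominator of the treatment-emergent ADA rate. The same patient would also leave the titer, neutralizing-status, onset and duration summaries.

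The stake is modest but real. Immunogenicity is a secondary objective. Someone who reads SAP 2.1.7 would take the reported rate to be conservative, when SAP 2.3.3 makes it complete-case. Two programmers could also build different ADA tables from the same SAP, depending on which section they followed. The primary efficacy analysis is not touched.

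**Working it through.** The plan states no figure on this point, so there is nothing to reproduce. The check is one of membership, followed by an illustration of size.

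**Step 1. Who triggers the rule, and who is in each population.** A treated patient falls into one of four cells.

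| Reportable baseline | Reportable post-dose | Rule in SAP 2.1.7 triggered | In SAP 2.3.3 population | In Protocol 11.3.3 population |
|---|---|---|---|---|
| No | No | No | No | No |
| No | Yes | **Yes** | **No** | **Yes** |
| Yes | No | No | No | No |
| Yes | Yes | No | Yes | Yes |

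Only the second cell triggers the rule. It is also the only cell on which the two populations differ. With a reportable baseline required, the rule acts on nobody in the SAP 2.4.7 summaries. With the protocol's population, it acts on everyone in that cell.

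**Step 2. Size.** Inputs:
- n = 47, the planned active arm (SAP 1.4). The active arm is the relevant one, because Protocol 9.3.1.3.2 tests placebo samples beyond baseline only when the baseline is positive.
- m, the share of patients with no reportable baseline. The documents give none; 0% to 10% is assumed.
- r, the ADA-positive rate. 5% to 25% is assumed. Inside that range lies 4/36 = 11.1%, from the single-dose study in healthy subjects (Protocol section 4).

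Formulas, treating m and r as independent:
- patients excluded = n × m
- expected positives lost = n × m × r
- chance of losing at least one = 1 − (1 − m × r)^n

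| m | Excluded | Positives lost, r = 5% | r = 11.1% | r = 25% | Chance of losing at least one, r = 11.1% |
|---|---|---|---|---|---|
| 0% | 0 | 0 | 0 | 0 | 0% |
| 2% | 0.94 | 0.05 | 0.10 | 0.24 | 10% |
| 5% | 2.35 | 0.12 | 0.26 | 0.59 | 23% |
| 10% | 4.70 | 0.24 | 0.52 | 1.18 | 41% |

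For example, 47 × 0.05 × 0.111 = 0.26. The largest value is 47 × 0.10 × 0.25 = 1.18.

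**Step 3. Why m is probably near the low end.** Under the general baseline definition, a patient whose Day 1 sample fails still has the Visit 1 sample. If each pre-dose sample failed independently with probability 5% (an assumption), both would fail in 0.05 × 0.05 = 0.25% of patients. That is 47 × 0.0025 = 0.12 patients, and at r = 11.1% about 0.013 positives. One provision points the other way: SAP 2.5.4 ties ADA results to the injection date within 2 days. If that disqualified the screening sample, m would be the Day 1 failure rate alone.

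**The case against.** The strongest reply is that the wording of SAP 2.3.3 leaves room for the rule. The requirement of a reportable result might attach only to the post-dose sample, so that a patient with a collected but non-reportable baseline stays in. Or a Visit 1 sample might satisfy SAP 2.3.3 while SAP 2.1.7 looks only at Day 1. Both readings are strained, and neither helps a patient with no pre-dose sample at all. They do mean that a reader who infers that the rule can never act goes further than the text allows.

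Three other inferences are tempting and not supported.
- *That seroconversions are lost.* Without a baseline, a positive result may be pre-existing antibody. What is lost is a positive that SAP 2.1.7 would classify as treatment-induced.
- *That the change from the protocol was concealed because SAP 1.6 does not list it.* That list covers changes made in the current SAP version, so the requirement may be older. Protocol 11.4.4 also leaves immunogenicity details to the SAP. The difference from Protocol 11.3.3 stands, but the silence of SAP 1.6 is weak evidence about its origin.
- *That the rate would fall from 5/47 (10.6%) to 4/46 (8.7%).* This supposes that an excluded patient is positive, and it rests on a single-dose rate in healthy subjects. Protocol section 4 also reports that weekly dosing up to 200 mg in patients with idiopathic pulmonary fibrosis produced no significant emergent ADA reactivity. That regimen is closer to the present one.

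It is also fair to say that requiring a baseline is a coherent choice when induced and boosted ADA must be told apart. It is not coherent alongside a rule for patients who have none. Finally, allergic and severe injection-site reactions are still captured as events of special interest on the safety population, whatever a patient's ADA status.

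**Conclusion.** The point holds as an internal inconsistency in the SAP. On its natural reading, SAP 2.3.3 excludes the patients for whom the SAP 2.1.7 rule is written, so the rate described as conservative becomes complete-case. It also narrows the protocol's population, which is compatible with the rule.

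The numerical effect is minor: an expected loss of about 0 to 1 ADA-positive patient of 47, and less if the Visit 1 sample can serve as baseline. That range rests on the assumed missing share (0% to 10%), the assumed ADA rate (5% to 25%) and independence of the two. It bears on a descriptive secondary summary only. This is a worthwhile tidy-up and does not threaten the trial's conclusions.

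**What to change.** In SAP 2.3.3, drop the baseline requirement and return to the protocol's definition: safety-population patients who have one or more reportable post-dose ADA results. The SAP 2.1.7 rule then has patients to act on. Add a footnote to the ADA tables giving, by arm, the number of patients whose baseline was set to negative.

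The cost is a few words and one footnote. Some pre-existing antibody may be counted as treatment-induced, which the SAP already accepts in calling the rule conservative; the footnote shows how many patients could be affected.

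If the sponsor prefers to keep the baseline requirement, delete the missing-baseline sentence from SAP 2.1.7 and state in the SAP that the ADA population departs from Protocol 11.3.3.

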2.3.4 Pharmacokinetics population

The PK population will include all randomized and treated patients (safety population) with at least one post-dose, non-missing plasma concentration value.

2.3.5 Biomarker population

Baseline biomarker population includes the randomized and treated patients with a baseline sample successfully analyzed.

Pharmacodynamics biomarker population includes the randomized and treated patients with a baseline sample and at least one post first double-blind IMP injection sample successfully analyzed.

2.4 STATISTICAL METHODS

Continuous data will be summarized using the number of available data, mean, SD, median, minimum, Q1, Q3 and maximum for each treatment group. Categorical and ordinal data will be summarized using the number and percentage of patients in each treatment arm.

2.4.1 Demographics and baseline characteristics

Parameters will be summarized on the randomized population analyzed in the treatment arm to which they were randomized. Analyses for the safety population will be included in the appendices if the size of the safety population is different (>10%) from the size of that in the primary analysis population for any treatment group.

Parameters described in [Section 2.1.1](#) will be summarized by treatment group and overall treatment groups using descriptive statistics.

The disease duration, mRSS, FVC and DLCO at baseline will be also summarized by stratification factor (as per IRT).

Medical/surgical history will be summarized in each treatment arm by primary SOC and PT. Events will be sorted by SOC internationally agreed order and decreasing frequency of PT based on the incidence in the overall treatment arm.

P-values on demographic and baseline characteristic data will not be calculated.

No specific description of the safety parameters will be provided at baseline. If relevant, the baseline values will be described along with each safety analysis.

No specific description of the efficacy parameters will be provided at baseline. If relevant, the baseline values will be described along with each efficacy analysis.

2.4.2 Prior or concomitant medications

The prior and concomitant medications will be presented for the randomized population.

Medications will be summarized by treatment group according to the WHO-DD, considering the first digit of the anatomic category (ATC) class (anatomic category) and the first 3 digits of the ATC class (therapeutic category). All ATC codes corresponding to a medication will be summarized, and patients will be counted once in each ATC category (anatomic or therapeutic) linked to the medication. Therefore patients may be counted several times for the same medication.

The table for prior medications will be sorted by decreasing frequency of ATC followed by all other therapeutic classes based on the overall incidence across treatment groups. In case of equal frequency regarding ATCs (anatomic or therapeutic categories), alphabetical order will be used.

Patients who received background therapy are defined as all patients who took a medication from the anatomic classes of “antineoplastic/immunomodulating agents” and/or “systemic hormonal preparations, excl. sex hormones and insulins” (see [Appendix J](#)) before and at baseline.

The second definition of patients who received background therapy is defined as all patients taken “methotrexate, mycophenolate mofetil, azathioprine, ciclosporin, and cyclophosphamide” (see [Appendix J](#)) before and at baseline.

The tables for concomitant and post-treatment medications will be sorted by decreasing frequency of ATC followed by all other therapeutic classes based on the incidence in the SAR156597 group. In case of equal frequency regarding ATCs (anatomic or therapeutic categories), alphabetical order will be used.

The patients who took a rescue medication during the study are defined according to the deviation “Prohibited use of immunosuppressive therapies as concomitant medications”.

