8.8.2 Key Authorized Concomitant Medications

- Oral corticosteroids are permitted if dose \leq 10 mg/day of oral prednisone or equivalent and at a stable dose for at least 4 weeks prior to the randomization (or baseline visit). No change in dose is permitted during the study unless for the management of an AE. Dose and any change will be recorded on the patient e-CRF. Oral corticosteroids cannot be started during the course of the study.
- Low dose immunosuppressive drugs (cyclophosphamide \leq 1 mg/kg oral/day or \leq 750 mg IV/month; azathioprine \leq 100 mg/day; methotrexate \leq 15 mg/week, mycophenolate mofetil \leq 2 g/day) are permitted if at stable dose for at least 4 weeks prior to randomization (or baseline visit). No change in dose is permitted unless for the management of an AE. Dose and any change will be recorded on the patient e-CRF. Low dose immunosuppressive drugs cannot be started during the course of the study.
- Calcium channel blockers, alpha blockers, prostaglandins, endothelin receptor antagonists, phosphodiesterase inhibitors, angiotensin receptor blockers, nitrate therapy, other vasodilators, and anti-platelets/anticoagulants for the treatment of Raynaud's phenomenon and/or digital ulcers are permitted during the course of the study.
- Vasodilators, endothelin receptor antagonists, phosphodiesterase inhibitors, calcium channel blockers, soluble guanylate cyclase stimulators (eg, riociguat) and anticoagulants for the treatment of controlled PAH are permitted during the course of the study.
- Angiotensin-converting enzyme inhibitors for prevention of scleroderma renal crisis are permitted during the course of the study.

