2.4.4.1.8 Subgroup analyses

To assess the homogeneity of the treatment effect across various subgroups, treatment-by-subgroup factor and time point-by-subgroup factor interaction terms and a subgroup factor term will be added in the primary MMRM model. Within each subgroup, baseline adjusted LSmeans estimates at Week 24 will be provided for both treatment groups with their corresponding SEs and 95% CIs, as well as their difference with the corresponding 95% and 90% CIs. Subgroups of interest are:

- Randomization stratum (as per IRT).
- Gender (male/female).
- Both Background therapy (yes/no) definitions defined in [Section 2.4.2](#).
- Disease duration of non-Raynaud's phenomenon (<20 months vs \geq 20 months).
- Auto antibodies (Centromere Antibodies, RNA Polymerase III Antibody, Scl-70 Antibody, [if size allows] and ANA staining pattern [Centromere vs. Non-Centromere staining pattern]).
- Geographical region (Estonia, Romania, Russia, Poland and Ukraine vs Rest of the World).

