Appendix J Codelists for background therapy definitions, AESIs and related hepatic disorder

Requested list	Type (cmq, smq, others)	Name or Code (cmqname, smqcd, others)	Description (cmqdesc or SMQ_ShortName, others)	Scope (smq) / prim_sec (soc)
Reqlist	Type	Codename	Desc	Scope
Background therapy definition 2	CDG	CDG00103	METHOTREXATE_mono_and_multiingredients	
Background therapy definition 2	CDG	CDG20046	MYCOPHENOLATE_MOFETIL_mono_and_multi_ingredients	
Background therapy definition 2	CDG	CDG00039	AZATHIOPRINE_mono_and_multi_ingredients	
Background therapy definition 2	CDG	CDG20011	CICLOSPORIN_mono_and_multi_ingredients	
Background therapy definition 2	CDG	CDG00040	CYCLOPHOSPHAMIDE_mono_and_multi_ingredients	
Background therapy definition 1	CDG	CDG00014	ANTINEOPLASTIC AND IMMUNOMODULATING AGENTS	
Background therapy definition 1	CDG	CDG10109	SYSTEMIC HORMONAL PREPARATIONS, EXCL. SEX HORMONES AND INSULINS	
Acute renal failure	SMQ	Acute renal failure (SMQ)	Acute renal failure Narrow	Narrow
Tuberculosis	CMQ	GLB_TUBERCULOSIS	Tuberculosis	
Anaphylactic reactions or acute allergic reactions that require immediate treatment	CMQ	Anaphylactic reaction Narrow	Anaphylactic reaction Narrow	
Hepatic disorder	SMQ	Hepatic disorders (SMQ)	Hepatic disorders Narrow	Narrow

Signature Page for VV-CLIN-0196174 v2.0
act14604-16-1-9-sap

Approve & eSign	[REDACTED]
	07-Mar-2019 16:13:03 GMT+0000

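### As named, background-therapy definition 1 counts any systemic hormone except sex hormones and insulins, so a patient on a non-corticosteroid hormone alone is classed 'yes' in a primary-endpoint subgroup

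*SAP*

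**What the plan says.** SAP 2.4.2 gives two definitions of background therapy. The first reads: "Patients who received background therapy are defined as all patients who took a medication from the anatomic classes of" two groups, the antineoplastic and immunomodulating agents and/or "systemic hormonal preparations, excl. sex hormones and insulins", taken before and at baseline. In describing the medication tables, the same section equates the anatomic category with the first digit of the ATC class, which is the broadest level it uses.

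Appendix J implements definition 1 with two codelists that carry the full class names: CDG00014, "ANTINEOPLASTIC AND IMMUNOMODULATING AGENTS", and CDG10109, "SYSTEMIC HORMONAL PREPARATIONS, EXCL. SEX HORMONES AND INSULINS". Neither place limits the hormonal class to corticosteroids, to an indication, or to drugs given for systemic sclerosis.

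The second definition ("The second definition of patients who received background therapy is defined as all patients taken" one of five named immunosuppressants) was added in this SAP version, according to SAP 1.6. It contains no hormone of any kind.

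SAP 2.4.4.1.8 lists "Both Background therapy (yes/no) definitions defined in" 2.4.2 among the subgroup factors to be added to the primary MMRM for change in mRSS at Week 24.

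On the protocol side, E 16 excludes high-dose or recently changed steroids, and 8.8.1 repeats this as a prohibition. Section 8.8.2 sets the permitted use ("Oral corticosteroids are permitted if dose" is low and stable) and gives parallel conditions for low-dose immunosuppressants. None of these sections mentions any other systemic hormone.

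**The concern.** The subgroup analysis asks whether the effect on mRSS is the same with and without background treatment. That question needs a 'yes' group made up of patients on treatment that could plausibly alter the disease or the response. Within the hormonal class, the protocol singles out corticosteroids alone for this purpose. Definition 1, as named, is wider than that.

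If some 'yes' patients take only an unrelated hormone, the 'yes' estimate becomes a mixture and moves toward the 'no' estimate, so real heterogeneity would be understated. The 'no' group also loses patients who belong in it, in a trial of only 94.

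Definition 2 does not fill the gap. It omits corticosteroids, so a patient on steroids alone is a 'no' under it. Neither definition therefore separates patients on a steroid or an immunosuppressant from patients on neither.

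**Working it through.** **The plan's own figure.** The only related figure is the power statement (Protocol 11.1, SAP 1.3): 47 per group, difference 3.6, SD 7, one-sided alpha 0.05.
- Standard error = 7 × √(2/47) = 1.444, and 3.6/1.444 = 2.493.
- Power = Φ(2.493 − 1.645) = 80.2%, or 79.7% with the noncentral t on 92 degrees of freedom.
- The plan states 80%, so it reproduces. Nothing below alters it.

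**Does the text take in a non-corticosteroid hormone?**
1. SAP 2.4.2 takes any medication from the named class.
2. The class name removes two things only: sex hormones and insulins.
3. Appendix J repeats the class name for CDG10109 and adds no restriction.
4. Thyroid hormone is a systemic hormone and is neither a sex hormone nor an insulin.
5. So, as named, a patient whose only qualifying drug is thyroid hormone is a 'yes'.

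**Direction of the error.** The rule is too inclusive. The error can only move patients from 'no' to 'yes', and it brings nobody into the 'no' group.

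**Possible size.** The documents give neither the number of such patients (m) nor the number classed 'yes' (N), so both are assumed here. Assume also that misplaced patients respond like 'no' patients and are spread evenly over the arms. The observed 'yes' effect is then a weighted mean:

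[(N − m) × d_yes + m × d_no] / N

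Subtracting d_no leaves (1 − m/N) × (d_yes − d_no). A true yes/no difference in effect therefore shrinks by the factor 1 − m/N.

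For precision, the 'no' group as classed has 94 − N patients and would have 94 − N + m if corrected. With the standard error proportional to 1/√n, it is inflated by √[(94 − N + m)/(94 − N)].

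| N classed 'yes' | m | m/N | Factor 1 − m/N | SE ratio, 'no' group |
|---|---|---|---|---|
| 30 | 1 | 3.3% | 0.967 | √(65/64) = 1.008 |
| 30 | 3 | 10.0% | 0.900 | √(67/64) = 1.023 |
| 30 | 10 | 33.3% | 0.667 | √(74/64) = 1.075 |
| 50 | 1 | 2.0% | 0.980 | √(45/44) = 1.011 |
| 50 | 3 | 6.0% | 0.940 | √(47/44) = 1.034 |
| 50 | 10 | 20.0% | 0.800 | √(54/44) = 1.108 |
| 70 | 1 | 1.4% | 0.986 | √(25/24) = 1.021 |
| 70 | 3 | 4.3% | 0.957 | √(27/24) = 1.061 |
| 70 | 10 | 14.3% | 0.857 | √(34/24) = 1.190 |

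With m = 0 both columns equal 1 and the problem has no practical effect.

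**The case against.** Several objections carry weight.

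- **The codelist contents are not printed.** Appendix J gives a code and a label. CDG10109 might already be limited to corticosteroids. A reader might infer that thyroid users are certainly counted, but the documents support only that they would be counted on the class name. This objection stands. If the list is in fact narrower, the text still needs to say so.
- **The size is unknown.** A reader might want a firm number of misclassified patients. The documents supply no basis for one, and the table above is conditional throughout.
- **The 'no' group is not biased.** It is tempting to say that the definition spoils the comparison free of background treatment. It does not: that group loses some precision, and only the 'yes' estimate is diluted.
- **The SAP already offers a narrower definition.** Definition 2 contains no hormones, both definitions are run, and medications are also tabulated at the three-digit therapeutic level. This helps a reader in part. However, definition 2 drops corticosteroids altogether, and tables by treatment group do not show who was on a hormone alone.
- **Protocol 8.8.2 is a list of key drugs and is not exhaustive.** It also allows vasodilators, endothelin receptor antagonists and other drugs for disease manifestations. It therefore cannot serve as a complete list of disease-directed treatment. In particular, it gives no ground for replacing CDG00014 with the immunosuppressants named there. Doing so could move patients on other permitted immunomodulators into 'no', which would contaminate a group that this error leaves clean.

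**Conclusion.** The point holds as a mismatch between the named hormonal class and the only systemic hormones the protocol controls as background treatment. As written, definition 1 would class a patient on a non-corticosteroid hormone alone as 'yes' in a planned subgroup analysis of the primary endpoint, and definition 2 does not repair this. The conclusion rests on the class name and on the absence of any stated restriction.

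The effect is a diluted 'yes' estimate and a somewhat smaller 'no' group. Its size cannot be derived from the documents and could be nil.

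A reader might infer that the trial's main result is at risk. It is not: the primary MMRM (SAP 2.4.4.1.1), the stratification and the sample size do not use this variable, and no decision rule depends on the subgroup result. This is an inexpensive improvement to one subgroup analysis.

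**What to change.** In SAP 2.4.2, restate the hormonal part of definition 1 as systemic corticosteroids. In Appendix J, replace CDG10109 with a systemic-corticosteroid codelist. If CDG10109 already contains only corticosteroids, say so and correct its label. Keep CDG00014 and definition 2 as they are. While editing, align Appendix B, which lists background therapy as a subgroup without saying which definition, with 2.4.4.1.8.

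The cost is one codelist and a few lines of SAP text. No new data are needed: SAP 2.1.2 already has all medications from 28 days before baseline recorded and coded in WHO-DD, and Appendix J already uses ingredient-level lists for definition 2. The change should be made before the first database lock (SAP section 4), so that group membership is fixed before the Week 24 results are seen.
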